7.2.2 Optum's Market Clarity Data

Beginning with the 2029 PSUR, patients will also be identified within Optum's Market Clarity Data. This database integrates medical and pharmacy claims data with clinical data for approximately 80-85% of patients in Optum's EHR Research Database from January 2007 through the present. Market Clarity includes data on over 82 million patients as of March 2024, with over 68 million of those having eligibility information available.

Optum's EHR Research Database is a patient-level database that integrates multiple electronic medical record data systems with medical billing, prescription, and practice management data. The database incorporates relevant clinical data, as recorded during routine clinical practice, for patients in both ambulatory and inpatient settings. Data include medical records, laboratory results, and drug prescription (including number of refills) and administration data.

The database also includes data derived from free-text clinical notes relating to the medical encounters. Optum uses a generalized natural language processing (NLP) system developed to extract and organize concepts from free text into semi-structured fields. The database contains pertinent attributes, sentiments, and modifiers to the concepts. Re-examination of the source text

corresponding to the NLP-extracted observations is possible with appropriate permissions.

In Market Clarity, Optum's EHR data are supplemented with medical and pharmacy claims from the ORD and from third-party data sources. The availability of linked pharmacy claims data in Market Clarity provides the opportunity to augment the data on drug prescriptions available in the EHR, which enables more comprehensive identification of all drugs received by patients through pharmacy drug dispensings. This linkage will accordingly improve the ability to capture nemolizumab initiation and subsequent drug dispensings within the database.

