7.3.2 Inclusion Criteria

Pregnancies among women who meet the following criteria will be eligible for inclusion in the study:

- An ECD between 12 August 2024 and 31 March 2032
- For claims data sources, continuous health plan enrollment with complete medical and pharmacy benefit coverage from 6 months before and including cohort entry (only applicable to the pregnant woman)
- For linked claims-EHR data sources:
 - Pharmacy (but not medical) coverage during the full pregnancy period (as described in [Table 1](#)) will be required to ensure dispensings of cohort defining drugs are captured. (A shorter period of continuous enrollment will be required for linked claims-EHR data sources compared with the claims databases because pharmacy claims will be used primarily for exposure assessment, while covariates will be assessed from the EHR data).
 - Presence of at least one outpatient clinical visit at least 6 months prior cohort entry (to establish a 6-month baseline period for assessment of AD and PN as well as clinical covariates).
- Evidence of moderate to severe AD or PN ascertained using appropriate algorithms

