Cohort entry will be set at the date of dispensing in the Nemolizumab Cohort (i.e., the earliest nemolizumab administration date during a pregnancy) and the Other AD/PN Treatment Cohort,

and the corresponding day of gestation among unexposed pregnancies, rounded down to the nearest week. For example, for pregnancies entering the Week 8 Cohort, we will first select all pregnancies with no nemolizumab or other AD/PN treatment from 5 times the half-life before ECD through 7 weeks' + 6 days' gestation. Then, we will assign the pregnancies that receive nemolizumab during Week 8 (8 weeks + 0 days through 8 weeks + 6 days) to the nemolizumab-exposed group, those that received another AD/PN treatment to the other treatment-exposed group, and those that did not receive nemolizumab or another AD/PN treatment during Week 8 to the unexposed group. Cohort entry among the Week 8 nemolizumab and comparator cohorts will be set to 8 weeks' + 0 days. The pregnancies in the Week 8 exposed cohort will no longer be eligible for inclusion in subsequent weekly cohorts. However, the pregnancies in the Week 8 unexposed group will go on to be eligible for inclusion in the Week 9 Cohort, at which point their exposure status would be reassessed during Week 9 (9 weeks + 0 days through 9 weeks + 6 days). A pictorial depiction of this process can be found in Figure 1 and key pregnancy dates can be found in Table 1. If the study size does not permit weekly sequential cohorts, the cohorts may be collapsed into longer (e.g., 2-week, 4-week) intervals as needed.

Figure 1 Sequential cohort design, depicting an example of cohort entry for the Week 7 and Week 8 cohorts

Abbreviations: AD, atopic dermatitis; ECD, estimated conception date; PN, prurigo nodularis

Table 1 Pregnancy dates

Date	Definition
LMP	First day of last menstrual period 0 gestational weeks ^{0/7 days}
Gestational age	Weeks of gestation Anchored by LMP Number of completed weeks elapsed after LMP

Date	Definition
ECD	Estimated as LMP + 14 days 2 gestational weeks ^{0/7 days}
First trimester	Begins at ECD minus 5 times the half-life of the treatment Ends at LMP + 97 days
Second trimester	Begins at LMP + 98 days Ends at LMP + 195 days
Third trimester	Begins at LMP + 196 days Ends at pregnancy outcome
Pregnancy period	Begins at ECD minus 5 times the half-life of the treatment Ends at pregnancy outcome

Abbreviations: ECD, estimated conception date; LMP, first day of last menstrual period

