7.7.4 Missing Data

This study is based on an analysis of automated medical and prescription claims. Data collected for administrative purposes, such as age (or date of birth) and sex, are not expected to be missing, and records with this information missing will not be used for analysis.

Using the standard approach in claims data analyses, the presence of a medication or diagnosis claim will be assumed to indicate use of that medication or the presence of that condition. Conversely, the absence of a medication or diagnosis claim will indicate the absence of use of that medication or a diagnosis of the condition. Therefore, covariates related to drug use and disease status will be categorized as yes (code present) or no (no code present) and there will be no missing data for these variables.

Within Optum's Market Clarity, an integrated claims-EHR data source, clinical variables are missing for some individuals because of variation in care practices. Health care encounters with medical providers who do not contract with Optum will not be observed. Because the EHR database is an open system, some patients may only receive a fraction of their care through a provider captured in the data, and medical encounters outside of the networks contributing data to the EHR database will not be observed. To mitigate the potential for missingness in the data, we will require that the study cohorts have evidence of routine care (i.e., at least one outpatient visit at least 6 months prior to the index date) within the contributing EHR systems. Patients meeting this criterion likely have a reasonably high capture of medical encounters in the data. Additionally, the EHR data in Optum's Market Clarity are supplemented with medical and pharmacy claims, likely improving the capture of clinical variables for most patients.

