11.4 Appendix D: Half-lives for Cohort Defining Treatments

Drug	Half-life	5 times half-life*	1.5 times half-life (sensitivity)*	3 times half-life (sensitivity)*
Dupilumab	2 weeks	10 weeks	3 weeks	6 weeks
Lebrikizumab	24.5 days	123 days	37 days	74 days
Nemolizumab	18.9 days	95 days (approximately 14 weeks)	29 days	57 days
Tralokinumab	3 weeks	15 weeks	32 days	9 weeks

*Numbers were rounded up to the nearest whole day.

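### In the linked claims-EHR sources, one outpatient visit at any time more than 6 months before entry does not show that a woman was observable during the 6-month baseline

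*Protocol*

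**What the plan says.** Protocol 7.3.2 sets two observability conditions for linked claims-EHR sources.

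- **Coverage.** The requirement is "Pharmacy (but not medical) coverage during the full pregnancy period". By Table 1 (7.3.6.1) that period "Begins at ECD minus 5 times the half-life of the treatment". The same bullet says that covariates will come from the EHR.
- **Prior contact.** The requirement is "Presence of at least one outpatient clinical visit at least 6 months prior cohort entry", and its stated purpose is "to establish a 6-month baseline period for assessment of AD and PN as well as clinical covariates".

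Section 7.7.4 acknowledges that the EHR is an open system in which only part of a patient's care may be seen. It then offers the same one-visit rule as the mitigation: "Patients meeting this criterion likely have a reasonably high capture of medical encounters in the data". For drug use and disease status it says that "the absence of a medication or diagnosis claim will indicate the absence of use of that medication or a diagnosis of the condition" and that these variables will have no missing data. Section 7.4.3, which covers both the claims databases and Market Clarity, uses the same yes/no coding.

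**The concern.** The visit rule has a lower limit only. A visit before the baseline shows that the woman was once in a contributing system. It does not show that she was still there during the 183 days in which her baseline is read. If she was not, her record is blank for that period and the blank is coded as no disease, no drug and no visits.

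These codes feed the propensity score and the weights (7.7.3.1). The balance check in that section uses the same recorded codes, so it cannot reveal that a covariate was captured better in one cohort than in another. None of the analyses in 7.7.3.5 tests baseline observability. If capture differs by cohort, weighting on the recorded covariate can leave confounding in place, or introduce a small difference where there was none.

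**Working it through.** The plan gives no figure for this point, so the check is whether any other criterion forces observed care in the baseline, followed by an illustration of size.

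**1. How old can the visit be?** Section 7.2.2 dates the linked data to the "EHR Research Database from January 2007 through the present". The longest covariate look-back is 5 years (7.4.3.2 to 7.4.3.5). For entry in August 2024 that look-back reaches August 2019, so a visit between January 2007 and August 2019, a span of over 12 years, meets the rule and lies outside every covariate window.

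**2. Does pharmacy coverage fill the gap?** For nemolizumab, Appendix D gives 5 half-lives as "95 days (approximately 14 weeks" (5 × 18.9 = 94.5, rounded up).

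- Entry at ECD: 95 of 183 baseline days are under required pharmacy coverage, and 183 − 95 = 88 are not.
- Entry at ECD minus 95 days: essentially none are.
- All 183 days are covered only from ECD + 88 days. With ECD at LMP + 14 days, that is LMP + 102 days, or 14 weeks + 4 days. This is later than the Week 2–13 cohorts used for the primary MCM analysis (7.3.6.2).

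The same arithmetic gives 10 weeks + 4 days for lebrikizumab, 13 weeks + 1 day for tralokinumab and 18 weeks + 1 day for dupilumab. Pharmacy coverage would not show diagnoses in any case.

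**3. Do the AD and PN criteria fill it?** The qualifying codes may fall anywhere from 12 months before ECD (AD, 7.3.4) or before pregnancy (PN, 7.3.5) to the end of pregnancy. Take entry at Week 8, which is ECD + 42 days (8 × 7 − 14). The baseline starts at about ECD − 140. That leaves roughly 365 − 140 = 225 days before the baseline, plus all the time after entry, in which two codes 30 days apart can sit. None need fall inside the baseline.

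**4. How does the plan treat silence elsewhere?** In Table 2, 8 weeks (56 days) without clinical activity counts as loss to follow-up in these sources. Before entry, 183 days of silence is accepted, which is 183/56 = 3.3 times as long.

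**5. Which covariates are exposed to this?** Comorbidities, pregnancy history and AD/PN history use up to 5 years (7.4.3.3 to 7.4.3.5), so older codes still count for a woman who was silent in the baseline. Utilisation uses up to 1 year (7.4.3.2); 183 silent days are half of 365. The loss therefore falls mainly on recent conditions, recent treatment and utilisation.

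**6. Illustrative size.** These inputs are assumptions, not taken from the protocol: one binary confounder with outcome RR 2, specificity 1, standardisation to the exposed, true prevalences pe and pu, and recording sensitivities se and su.

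Residual RR = [1 + pe(RR − 1)] / [pe·se·RR + (1 − pe·se)(1 + q(RR − 1))], where q = pu(1 − su)/(1 − pu·su) is the true prevalence among unexposed women without a code.

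- pe = pu = 0.30, se = 0.9, su = 0.5: q = 0.15/0.85 = 0.176; 1.30/(0.54 + 0.73 × 1.176) = 1.30/1.399 = 0.93, where the truth is 1.00.
- pe = pu = 0.20, same sensitivities: q = 0.10/0.90 = 0.111; 1.20/(0.36 + 0.82 × 1.111) = 1.20/1.271 = 0.94.

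**The case against.** The strongest reply is that the propensity score is mostly not built on the 183-day window. A woman silent for six months still contributes up to five years of diagnoses and treatments. Every woman also needs repeated AD or PN codes around the pregnancy, so one visit long ago and nothing since is an edge case of unknown frequency. This stands, and it limits the harm to recent information. It does not make the rule do what it is stated to do.

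Differential capture is also an assumption. Unexposed women with AD and no qualifying biologic or JAK inhibitor dispensing must qualify through repeated dispensings, and under one criterion through dermatologist or allergist codes (7.3.4), so they are not plainly low-contact. Users of the comparator biologics need prescribing contact as well. A reader might infer that both comparisons are affected alike; the protocol gives no ground for that, and the concern is mainly Nemolizumab versus Unexposed.

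The plan has partial mitigations: visit counts are candidate propensity covariates, claims supplement the EHR where present, a bias analysis for unmeasured confounding is planned (7.7.3.5.6), and sources are analysed separately before meta-analysis. The ORD requires six months of full medical and pharmacy coverage, so it is unaffected and offers a contrast. None of these identifies women whose baseline was unobserved, and the visit counts are themselves affected by the gap.

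A reader might also infer that ordinary under-recording belongs to this defect. With 50% capture in both cohorts and true prevalence of 30% versus 15%, crude confounding of 1.13 is reduced only to 1.07. That would arise under any visit rule and should not be charged to this one.

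**Conclusion.** The point holds on the text. In linked claims-EHR sources the visit rule does not establish an observed baseline, no other criterion does so in its place, and 7.7.4 cites the rule as evidence of good capture while coding every blank as no.

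Its size cannot be computed: the protocol gives neither the share of women without baseline contact nor capture by cohort. The figures of 0.93 and 0.94 rest on an assumed 90% versus 50% capture and show only the order of effect per covariate. It would be tempting to read them as an expected bias towards reassurance, or to conclude that the weighting is generally invalid. The documents support neither: the look-backs are long, the direction depends on which cohort is better captured, and the study is sized for MCM relative risks of 2.5 to 3. This is a cheap improvement, not a threat to the study's main conclusion.

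**What to change.** In 7.3.2, and in the matching sentence of 7.7.4, do one of the following.

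- **Tighten the rule.** Bound the earlier visit, for example to 6 to 12 months before cohort entry, and require at least one encounter, or medical-claims coverage, within the 183-day baseline.
- **Keep the wider population.** Add a sensitivity analysis restricted to women with observed baseline contact, and report by cohort the share without it.

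In either case, qualify the 7.7.4 sentence on capture so that it claims only what the chosen rule shows.

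The cost is a sentence or two and one programming filter. Market Clarity enters with the 2029 PSUR, and matching and propensity scores wait for the final report, so no comparative analysis would need redoing. The downside of tightening is some loss of linked-source pregnancies with sparse contact, and some selection towards women in care if the restriction applies in the main analysis. The second option avoids both in the main analysis.

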7.3.3 Exclusion Criteria

7.3.3.1 JAK Inhibitors

Pregnancies among women exposed to oral JAK inhibitors indicated for moderate to severe AD or PN (i.e., abrocitinib, upadacitinib, baracitinib) from 5 half-lives (specific for each medication) prior to ECD through the end of pregnancy will be excluded because they are contraindicated

during pregnancy. This list may be updated if other JAK inhibitors are approved for moderate to severe AD or PN during the study period.

7.3.3.2 Concurrent Exposure to Nemolizumab and Other AD/PN Treatments

Pregnancies among women with claims for both nemolizumab and another AD/PN Treatment during the relevant exposure window will be excluded.

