For the final report, pregnancies exposed to nemolizumab and their matched comparators will be identified in the selected databases. The final report analyses will employ a target trial emulation approach using a sequential matched cohort design that aligns cohort entry by gestational week (Caniglia et al., 2023; Hernández-Díaz et al., 2023). Nemolizumab-exposed pregnancies will be 1:4 matched to comparator pregnancies based on maternal age at cohort entry, gestational week of dispensing, indication, and calendar week. The frequency of pregnancy and infant outcomes among nemolizumab-exposed pregnancies and comparator pregnancies will be calculated. In the comparative analysis, pregnancies among patients with moderate to severe AD or PN who were

exposed to nemolizumab will be contrasted with the comparator groups using stabilized inverse probability of treatment weighting (IPTW) to adjust for potential confounding. RRs will be estimated using robust Poisson regression models and HRs using Cox proportional hazards models.

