7.3.6 Study Population

7.3.6.1 Exposure Cohorts and Cohort Entry

[figure not shown]
Based on the sequential cohort design, a series of study cohorts will be established for each gestational week of pregnancy ([Caniglia et al., 2023](#); [Hernández-Diaz S et al., 2023](#)). To ensure capture of exposure to AD/PN treatments prior to the ECD but which remain in the body at ECD, the first gestational week of pregnancy will be extended (prior to ECD) by 5 times the half-life for each AD/PN treatment. For example, since nemolizumab has a half-life of 18.9 days ([Nemluvio PI, 2025](#)), the first gestational week for nemolizumab will begin 95 days (approximately 14 weeks) prior to ECD. The half-life for each AD/PN treatment is provided in [Appendix D](#).

As nemolizumab and the comparator AD/PN treatments are injection drugs that are dispensed at a pharmacy for self-injection, treatment duration will be defined as date of dispensing plus 5 times the half-life of the therapy when a single pre-filled syringe, pen, or autoinjector is dispensed. When multiple units are dispensed, the days' supply will be calculated based on the quantity dispensed and recommended administration schedule; treatment duration will be calculated as the date of dispensing plus the days' supply plus 5 times the half-life of the therapy. A treatment will be considered to be overlapping with the first gestational week of pregnancy if there is at least one dispensing or dose received during the period 5 times the half-life prior to ECD through the end of the first gestational week. At each gestational week, we will first restrict to eligible pregnancies with no administrations or dispensings of nemolizumab or the other AD/PN treatments from 5 times the half-life of the corresponding treatment (e.g., 95 days, or approximately 14 weeks, for nemolizumab) before ECD through the end of the prior gestational week. We will then classify exposure status as exposed to nemolizumab, exposed to other AD/PN treatments, or unexposed based on the pregnancy's receipt of nemolizumab or other AD/PN treatments during that gestational week. Pregnancies among women with claims for both nemolizumab and another AD/PN treatment during the relevant exposure window will be excluded. For exposed pregnancies with more than one dose of the index treatment (e.g., two doses of nemolizumab) during pregnancy, cohort entry will align with the first dose.

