7.3.6.3 Nemolizumab Cohort

The Nemolizumab Cohort will include all pregnancies among women with moderate to severe AD or PN and at least one dispensing or dose of nemolizumab from 95 days (approximately 14 weeks) prior to ECD through the end of pregnancy. Cohort entry will be set at the date of the first nemolizumab dispensing, rounded down to the nearest week of gestation.

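### The both-drug exclusion and the unexposed definition use claims after cohort entry, so they select on pregnancy survival and conflict with the sequential design

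*Protocol*

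**What the plan says.** Protocol 7.1 describes the final analysis as a "target trial emulation approach using a sequential matched cohort design". Under 7.3.6.1 each weekly cohort admits only pregnancies with "no administrations or dispensings of nemolizumab or the other AD/PN treatments from 5 times the half-life of the corresponding treatment" before conception up to the end of the preceding week. Then: "We will then classify exposure status as exposed to nemolizumab, exposed to other AD/PN treatments, or unexposed", according to what is received in that week. With repeat doses, "cohort entry will align with the first dose". Once exposed, a pregnancy leaves the pool: "The pregnancies in the Week 8 exposed cohort will no longer be eligible for inclusion in subsequent weekly cohorts". Unexposed pregnancies stay in it and are reassessed the following week.

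The exclusion sits on top of this. Section 7.3.3.2, headed as concurrent exposure, says: "Pregnancies among women with claims for both nemolizumab and another AD/PN Treatment during the relevant exposure window will be excluded". Section 7.3.6.1 repeats it. Neither place says which window is meant or limits it to claims at or before cohort entry. Table 2 has a column of etiologically relevant exposure windows, set by outcome: first trimester, conception to 19 weeks + 6 days, conception to 36 weeks + 6 days, or the whole pregnancy. The Nemolizumab Cohort in 7.3.6.3 requires "at least one dispensing or dose of nemolizumab from 95 days (approximately 14 weeks) prior to ECD through the end of pregnancy".

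Section 7.3.6.5 defines the Unexposed Cohort by the absence of all four study biologics until the pregnancy ends.

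**The concern.** A target trial assigns treatment at time zero and keeps everyone assigned. Here a pregnancy can be deleted for a claim made weeks after time zero. Take a woman who enters the Nemolizumab Cohort at Week 2 and starts dupilumab at Week 16: she is removed from the spontaneous-abortion analysis. Had she miscarried at Week 10, she would have stayed in, because she never had time to switch. Removing pregnancies that survived long enough to switch raises the apparent risk of early loss. Weighting on baseline covariates cannot undo selection on later events.

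The rule is also uneven. A nemolizumab user is dropped for moving to any of three drugs (7.3.6.4). A comparator user is dropped only for moving to nemolizumab; a change from dupilumab to tralokinumab stays in. The unexposed are selected through 7.3.6.5, which drops women who later start a biologic, although 7.3.6.1 keeps such pregnancies in the unexposed group of earlier weeks. At stake are the pregnancy-loss estimates of a safety study, where a false signal or a hidden one matters.

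**Working it through.** **The timing of the claims.** Entry is at the first dose, and any study biologic before the entry week makes the pregnancy ineligible. The second drug must therefore fall in the entry week (for the first weekly cohort, this includes the extension before conception) or later. Switching is not a censoring event in Table 2 or 7.3.6.7. None of the sensitivity analyses in 7.7.3.5 and no limitation in 7.10 deals with it.

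**The plan's own figures.** The two-proportion formula (pooled variance, no continuity correction, 1:4, two-sided 0.05, 80% power) returns the stated 214 exposed live births for malformations at RR 2.5, and 77/37/22 for spontaneous abortion at RR 2/2.5/3. Then 214/(0.80 × 0.76) = 351.97, so 352 pregnancies, and 4 × 352 = 1,408. No stated figure is in dispute.

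**Size of the distortion.** Inputs: spontaneous-abortion prevalence p = 0.14 (Table 3); at-risk weeks 2 to 19 (Table 2), T = 18. Assumptions: no true effect, constant and independent hazards, and a share s who would switch by the end of Week 19 if the pregnancy continued. The protocol gives no s; 5% to 30% is shown.

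- Loss hazard λ = −ln(1−p)/T; switch hazard γ = −ln(1−s)/T.
- Ongoing and not switched: S = (1−p)(1−s).
- Lost before switching: L = λ/(λ+γ) × (1−S).
- Observed risk after the exclusion = L/(L+S); share removed = 1−(L+S).

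For s = 0.10: S = 0.86 × 0.90 = 0.774; λ/(λ+γ) = 0.1508/0.2562 = 0.589; L = 0.589 × 0.226 = 0.133; risk = 0.133/0.907 = 14.7%; removed = 9.3%.

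| Assumed s | Observed risk | RR against unselected 14% | RR if comparator switches at half the rate | Share removed | Exposed needed to keep 352 |
|---|---|---|---|---|---|
| 5% | 14.3% | 1.02 | 1.01 | 4.6% | 370 |
| 10% | 14.7% | 1.05 | 1.02 | 9.3% | 389 |
| 20% | 15.5% | 1.10 | 1.05 | 18.6% | 433 |
| 30% | 16.4% | 1.17 | 1.09 | 28.0% | 489 |

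The last column is 352/(1 − share removed), rounded up. With equal switching in both cohorts the RR is 1.00.

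A simulation with 1,000,000 pregnancies per arm gives rate ratios, closer to the planned Cox hazard ratio, of 1.03/1.05/1.12/1.20 against an unselected comparator. Keeping these pregnancies and censoring at the switch returns 0.99 to 1.00 in every scenario, under independent switching.

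The same formula with p = 0.01 for stillbirth and the same s applied from Week 20 gives 1.03/1.05/1.12/1.20%: a similar ratio but a far smaller absolute change.

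**Changing only the exclusion.** If 7.3.3.2 and 7.3.6.1 were corrected and 7.3.6.5 left alone, the exposed cohort would show 14.0%. At 10% later initiation the unexposed would show 14.7%. The ratio is 0.1400/0.1467 = 0.95, a bias that hides harm.

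**The case against.** The phrase is undefined, the heading says concurrent, and in 7.3.6.1 the sentence comes just after the rule that classifies by receipt within the gestational week. It could therefore mean both drugs in the entry week, in which case nothing is selected on the future. That reading is possible, but the text does not state it. Table 2 and the cohort definitions, which run to the end of pregnancy, point the other way. The window has to be defined in either case.

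A reader might infer a larger bias from p/(p + (1−p)(1−s)), which gives 15.3/16.9/18.9%, or RR 1.09/1.21/1.35, for s of 10/20/30%. That formula assumes no pregnancy ending in loss is ever preceded by a switch. Some would be, and they would be excluded too, so these values are upper bounds and not estimates.

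A reader might also infer that both main contrasts are biased against nemolizumab. The documents do not support this. The Other AD/PN Treatment Cohort is under the same rule, and the unexposed are selected by 7.3.6.5. Cancellation against the active comparator needs equal exclusion rates, and the uneven rule gives no reason to expect them, but the direction cannot be derived.

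It is also fair to say that the primary outcome is largely spared. Malformations are assessed among linked live births, so keeping early losses does not enter that comparison. There the cost is fewer exposed pregnancies. That still matters: Table 4 shows 209 pregnancies with an atopic dermatitis code and a dupilumab dispensing from 2020 to part of 2024, against a target of 352 exposed.

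**Conclusion.** The point holds as a design fault in wording that spans several sections. On the reading that Table 2 supports, 7.3.3.2 and 7.3.6.1 condition cohort membership on claims after time zero, and 7.3.6.5 does the same for the unexposed and contradicts the weekly reassessment in 7.3.6.1. The outcomes affected are those followed during pregnancy, chiefly spontaneous abortion and elective termination, and to a lesser degree stillbirth and preterm birth.

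Under the stated assumptions, one cohort's spontaneous-abortion risk is inflated by a factor of 1.02 to 1.17 for switching of 5% to 30%. The distortion in a planned contrast is smaller when the comparator is similarly selected and nil when selection is equal. Its net direction is unknown because no switching or later-initiation rates are given. These ratios are small beside the RRs of 2 to 3 for which the study is sized. The case for acting is that the selection is avoidable by wording alone.

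**What to change.** Change the sections together:

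- In 7.3.3.2 and the matching sentence of 7.3.6.1, limit the both-drug exclusion to claims on or before the end of the cohort-entry week (for the first weekly cohort, including its extension before conception).
- In 7.3.6.5, define unexposed status by no study biologic up to and including the entry week, in line with the weekly reassessment in 7.3.6.1.
- Treat a later switch or initiation identically in all three cohorts: followed as assigned, or censored at the switch. Name one as the main analysis and the other as a sensitivity analysis, and add the censoring event to Table 2 and 7.3.6.7 for the analysis that uses it.
- Report the number of later switchers and initiators per cohort.

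This needs no new data and keeps exposed pregnancies that would otherwise be lost. The costs are that some later cross-exposure remains in the as-assigned analysis and may dilute an effect, and that censoring at the switch may be informative and may need weights. A pregnancy may also appear as unexposed in one week and exposed in a later one, so the variance should allow for this.
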